16.1.3.3 Blood Cultures

Two sets of blood cultures (1 set = 1 aerobic bottle + 1 anaerobic bottle) should be collected within the 24 hours prior to the first dose of test article. Each set of blood cultures should be collected by direct venipuncture from independent body sites at least 15 minutes apart. Blood cultures should be collected for subjects that are clinical failures at the EOT and/or PTE visit. If bacteria are isolated from blood cultures, repeat blood cultures should be collected. If subsequent blood cultures are also positive, repeat the blood cultures as necessary until negative blood cultures are obtained (see [Section 8](#)). Blood culture isolates should be sent to the Central Laboratory (see [Section 17.3](#)).

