5.2.2.2 Microbiologic Outcomes

Microbiological response definitions for the evaluations performed at the EOT and PTE Visits and analyzed in the micro-mITT and ME populations are presented in Table 3 below. At the EOT and/or PTE visit, infection site specimen cultures and Gram stains should be obtained only for subjects who are clinical failures and require alternative antibacterial treatment for the infection under study.

If a subject has the same pathogen (ie, same genus and species) identified from both an ABSSSI and blood specimen, a microbiological response is determined for each of the pathogens. For tables summarizing microbiologic response for pathogens from the ABSSSI or blood specimen, if the same pathogen is isolated from both an ABSSSI and blood specimen, the worst response is summarized. The microbiologic response for the ABSSSI pathogen is based on the pathogen isolated from the EOT or PTE specimen, if a specimen was collected. The microbiologic response for the blood pathogen is based on the blood sample collected at EOT or PTE, or if a sample was not collected at the post-baseline visit, the blood sample collected prior to and closest to the visit.

Table 3. Per-Pathogen Microbiological Response Definitions at the EOT and PTE Visits

Term	Definition
Eradication	Absence of original baseline pathogen
Presumed Eradication	No source specimen to culture in a subject assessed with a clinical success by the Investigator
Persistence	Continued presence of the original baseline pathogen
Presumed Persistence	No source specimen to culture in a subject assessed with a clinical failure by the Investigator
Indeterminate	The subject's clinical response is indeterminate or other circumstance that precludes a microbiological evaluation

EOT = end of treatment; PTE = post-therapy evaluation.

Microbiological outcomes are further categorized as favorable, unfavorable and indeterminate. Favorable microbiological outcomes are defined as eradication or presumed eradication. Unfavorable microbiological outcomes are defined as persistence or presumed persistence. Microbiological response will be derived using electronic microbiology data from the central laboratory (or local laboratory if central data are not available) and from pathogen determination provided by the sponsor for each baseline isolate.

Overall microbiological response at PTE is determined as follows ([Table 4](#)) from the microbiological responses at the EOT and PTE Visits:

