 - Subjects will be defined as an Indeterminate if the investigator cannot determine whether the subject is a Clinical Success or Failure at the EOT or PTE Visits or the subject has a missing response. By definition, subjects with an Indeterminate response are included in the denominator for analyses in the mITT and micro-mITT populations, and thus, are considered Clinical Failures. Subjects with an Indeterminate response are excluded from the CE-EOT, CE-PTE, ME-EOT and ME-PTE populations.

- For microbiologic response:
 - If no source specimen is obtained and the subject has an investigator's assessment of Clinical Response, the per-pathogen microbiological response is based on the investigator's assessment of Clinical Response (ie, the response is a presumed response). A per-pathogen microbiological response at the EOT Visit or PTE Visit will be considered Indeterminate only if the Clinical Response at EOT or PTE is also Indeterminate.
- Missing values for other individual data points will remain as missing. Missing values will not be imputed and only observed values will be used in data analyses and presentations.
- Where individual data points are missing, categorical data will be summarized based on reduced denominators (ie, only subjects with available data will be included in the denominators).

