- ⁿ Blood pressure and pulse rate should be measured within 30 min before, and approximately (\pm 15 minutes) 1 hour after and 3 hours after the completion of the odd numbered doses on Days 2 and 3. In the event that the subject takes the dose before arriving for the office visit, the site should collect the 1 and 3 hour post dose measurements if possible, if not then a single measurement should be made at any time during the visit and the date and time recorded.
- ^o A 12-lead ECG should be performed at screening, at the EOT visit, and as otherwise clinically indicated.
- ^p A urine dipstick test will be performed locally at Screening.
- ^q All women will have a local urine pregnancy test at Screening.
- ^r All women will have blood collected for a serum β -hCG pregnancy test at the Central Laboratory at the Screening, EOT and PTE visits.
- ^s Blood will be collected for hematology (includes coagulation) and serum chemistry testing at the Central Laboratory at Screening and at the Day 3, Day 7, Day 10, EOT and PTE visits.
- ^t At the Screening visit, blood will be collected for local laboratory hematology and serum chemistry evaluations required for assessing subject eligibility.
- ^u If bacteria are isolated from blood cultures, repeat blood cultures should be collected. If subsequent blood cultures are also positive, repeat the blood cultures as necessary until negative blood cultures are obtained.
- ^v At the EOT and/or PTE visit, blood cultures and infection site specimen cultures and Gram stains should be obtained only for subjects who are clinical failures and require alternative antibacterial treatment for the infection under study.
- ^w A subject's AEs and SAEs will be recorded and reported from signing of the ICF to the Final Follow-up assessment.
- ^x A 6 hour fast is required before and a 2 hour fast is required following all odd numbered doses. The total duration of test article therapy for all subjects will be 7 to 14 days. Test article may be dispensed and reconciled by blinded personnel. Subjects will be asked to return all unused test article and packaging at each visit. At the EOT visit subjects will return the test article packaging and site staff will perform accountability.
- ^y Subjects should receive their first dose of test article at the site within 4 hours after randomization.
- ^z Subjects should be instructed not to take the odd numbered dose on Day 2 until they return to the site for the Day 2 visit.

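### The blood-culture fall-back in SAP 5.2.2.2 is not limited to post-baseline samples, so it conflicts with Table 3 and SAP 8.3 for a bacteremic subject who was never re-cultured

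*SAP*

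**What the plan says.** **Fall-back for blood pathogens.** SAP 5.2.2.2 takes the response for a blood pathogen from the EOT or PTE blood sample or, "if a sample was not collected at the post-baseline visit, the blood sample collected prior to and closest to the visit". The sentence sets no earliest date for that sample. The matching rule for the infection site has no look-back.

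**Response definitions.** SAP Table 3 defines Persistence as "Continued presence of the original baseline pathogen" and Presumed Eradication as "No source specimen to culture in a subject assessed with a clinical success by the Investigator".

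**Missing data.** SAP 8.3 states: "If no source specimen is obtained and the subject has an investigator's assessment of Clinical Response, the per-pathogen microbiological response is based on the investigator's" clinical assessment ("ie, the response is a presumed response"). It makes no exception for blood.

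**When cultures are taken.** Under SAP Appendix 1, at EOT and PTE "blood cultures and infection site specimen cultures and Gram stains should be obtained only for subjects who are clinical failures" who need alternative antibacterial treatment. Protocol 16.1.3.3 agrees: "Blood cultures should be collected for subjects that are clinical failures at the EOT and/or PTE visit". The same protocol section adds: "If bacteria are isolated from blood cultures, repeat blood cultures should be collected", and it continues this until cultures are negative. The SAP schedule repeats that instruction.

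**The concern.** A bacteremic subject who is a clinical success will normally have no EOT or PTE blood culture, so the fall-back is the usual route for that subject. If no repeat culture was drawn either, the nearest earlier blood sample is the positive baseline culture. The literal rule then turns the absence of a repeat culture into a documented microbiological failure, while two other rules in the same SAP call the subject presumed eradicated.

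At stake are the per-pathogen and per-subject microbiologic rates, and above all the separate summary of blood pathogens in SAP 10.4, where numbers are likely to be small. Two programmers could follow the SAP faithfully and produce different tables.

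**Working it through.** No figure stated in the plan depends on this rule, so there is none to reproduce. The check traces the rules and then shows a range under stated assumptions.

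**1. What the fall-back can return.** A subject with a blood pathogen has at least one earlier blood sample, namely the one that grew it. Read literally, the search for the closest earlier sample is therefore never empty. Table 3's presumed categories and the SAP 8.3 rule could then never apply to a blood pathogen.

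**2. Two readings, for a subject with a positive baseline blood culture and no EOT/PTE sample.** Reading A is the literal fall-back. Reading B allows only post-baseline samples and otherwise applies Table 3 and SAP 8.3.

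| Clinical response | Later blood cultures | Reading A | Reading B |
|---|---|---|---|
| Success | none | Persistence | Presumed Eradication |
| Failure | none | Persistence | Presumed Persistence |
| Indeterminate | none | Persistence | Indeterminate |
| Any | last one negative | Eradication | Eradication |
| Any | last one positive | Persistence | Persistence |

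The readings differ only when there is no later blood culture. Only the clinical success then moves from favorable to unfavorable. A failure is unfavorable under both. An indeterminate subject changes category, but SAP 10.4 tabulates indeterminate with unfavorable in the micro-mITT, so the favorable rate there does not move.

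**3. How the result carries forward.** Under SAP 5.2.2.2 the worst response counts when blood and site share a pathogen, and one unfavorable pathogen makes the subject unfavorable. Under Tables 4 and 5, unfavorable at EOT remains unfavorable at PTE.

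**4. Size, under assumptions.** The documents give no bacteremia rate, no micro-mITT size and no share of subjects without a repeat culture. Let b be the bacteremic share of the micro-mITT, r the share of these without a repeat culture, and s the share of those who are clinical successes. If all of them would otherwise be favorable:

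fall in per-subject favorable rate = b × r × s

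The micro-mITT size cancels. Here s is set to 85%, the planning rate for clinical success at PTE in the mITT (SAP 5.1.1); b and r are assumed.

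| | r = 10% | r = 50% | r = 100% |
|---|---|---|---|
| b = 1% | 0.085 points | 0.425 | 0.85 |
| b = 3% | 0.255 | 1.275 | 2.55 |
| b = 5% | 0.425 | 2.125 | 4.25 |

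The right-hand column supposes that no bacteremic subject was ever re-cultured, so it is an outer limit for each b.

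**5. The bacteremic-only table.** As an illustration, if 2% of 704 subjects were bacteremic (704 × 0.02 ≈ 14, or 7 per arm), one reclassified subject would move that arm's rate by 1/7 ≈ 14 points. Any single reclassification in so small a group would do the same.

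**The case against.** A reader might infer that the SAP settles the matter and scores bacteremic clinical successes as Persistence. The documents do not support that, for two reasons.

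- **Precedence is open.** Persistence requires continued presence, and the baseline culture, which only identifies the pathogen, cannot show that on its own. SAP 8.3 supplies a presumed response with no exception for blood. A coherent reading therefore exists: use the nearest post-baseline sample and otherwise the presumed response.
- **The triggering case departs from the plan.** Positive blood cultures are to be repeated until negative. The fall-back evidently serves to pick up that repeat culture, and for a subject followed as planned it works.

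A reader might also infer a threat to the trial's conclusions. There is none. Non-inferiority is tested on Early Clinical Response in the mITT population (SAP 10.1), and the investigator's assessment at PTE does not use culture results. SAP 10.4 describes its confidence intervals as descriptive and draws no non-inferiority conclusion from them. The rule is the same in both arms, and the isolate listing in SAP 9.2.1 would make an affected case traceable.

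All of this limits the reach of the point, but it does not remove the conflict. The repeat-culture instruction is worded as something that should be done, and a missing-sample rule exists for cases where it was not. The SAP nowhere ranks the fall-back against Table 3 or SAP 8.3. The stated tasks of the Evaluability Review Team (SAP 6.2) are population inclusion and pathogen status, so no stated review step would catch a response derived from a baseline culture.

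**Conclusion.** The concern holds as an unresolved conflict between rules. For a bacteremic clinical success with no repeat culture, SAP 5.2.2.2 read literally can give Persistence, while Table 3 and SAP 8.3 give Presumed Eradication. For an indeterminate subject the split is Persistence against Indeterminate. This is more than missing detail, because a stated rule contradicts another for an identifiable subject.

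The case is narrow and the effect is confined to descriptive per-subject and per-pathogen microbiologic results, mainly the bacteremic-only table. The documents do not allow the size to be determined. The range of about 0.1 to 4.3 points in the per-subject favorable rate rests entirely on the assumed bacteremia, no-repeat and success shares, and no tighter upper bound can be defended from the text.

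**What to change.** Before unblinding, replace the fall-back in SAP 5.2.2.2 with:

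*The last blood sample collected after the first dose of test article and after the sample that defined the baseline pathogen, on or before the visit; if there is none, the presumed response in Table 3 and Section 8.3 applies. The sample that defined the baseline pathogen can never supply a post-baseline response.*

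Both date conditions are needed. SAP 6.1.4 and 8.2 allow a Day 2 or Day 3 sample to serve as baseline in cellulitis/erysipelas, so a condition on the first dose alone could readmit the sample that defined the pathogen.

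The cost is this short text change and the matching date condition in the derivation program. No new data are needed, and results for subjects with a true post-baseline blood culture do not change. Making the change before unblinding ensures that the choice of rule cannot depend on the results.

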5.3 Safety Measures

The safety parameters include AEs, clinical laboratory evaluations, vital signs, and ECG findings. AEs will be coded using the Medical Dictionary of Regulatory Activities (MedDRA) Version 17.1 or higher to the System Organ Class and Preferred Term levels.

5.4 Pharmacokinetic Parameters

The concentration of omadacycline will be obtained from plasma samples. Refer to the pharmacokinetic analysis plan for further details.

6 STUDY POPULATIONS

6.1 Analysis Populations

6.1.1 Intent-to-Treat (ITT) Population

The ITT population will consist of all randomized subjects regardless of whether or not the subject received test article. A subject is considered randomized when the IxRS provides the test article assignment by providing the kit number (ie, completes a randomization transaction).

6.1.2 Safety Population

The Safety population will consist of all randomized subjects who receive test article. All safety analyses will be conducted in this analysis set.

6.1.3 Modified Intent-to-Treat (mITT) Population

The mITT population will consist of all randomized subjects without a baseline sole Gram-negative ABSSSI pathogen. Pathogen determination is described in Section 6.1.4.

6.1.4 Microbiological Modified Intent-to-Treat (micro-mITT) Population

The micro-mITT population will consist of all subjects in the mITT population who have at least one Gram-positive causative bacterial pathogen identified from a blood culture or from a culture of a microbiological sample obtained from the primary ABSSSI site at baseline using a valid sampling technique. Pathogen determination is based on the genus and species identification from the central laboratory. If the local laboratory grows an acceptable pathogen but the central laboratory is not able to grow the isolate, if isolates are lost during transportation or storage, or there are major discrepancies between the local and central laboratory in the identification of species, the central laboratory or other Sponsor designee will request that the local laboratory resend the isolate. If the central laboratory cannot determine the genus and species of the isolate for any reason, the local laboratory determination of genus and species will be used for pathogen identification. The central laboratory identification of genus and species is used for analysis unless no central determination exists in which case the local laboratory determination is used. If the central lab does not speciate the pathogen but the local/regional lab does speciate the pathogen, the Sponsor will make the final determination as to which pathogen identification is used for analysis.

An acceptable ABSSSI site specimen obtained via a valid sampling technique is defined as one obtained from a biopsy of involved cutaneous or subcutaneous tissue preferably from the advancing margin of the lesion, debrided tissue, tissue scraping (using curette or scalpel), needle aspirate of involved, nonpurulent cutaneous or subcutaneous tissue, pus or infected tissue collected during an incision and drainage procedure, pus aspirated into a syringe or a deep swab of purulent material (only if collected from infected tissue that has been incised or is draining). Surface swabs of wounds, inflamed skin or drainage (including purulent material) are not considered valid sampling techniques. If more than one baseline ABSSSI site sample was obtained using a valid sampling technique or more than one baseline blood sample was obtained, isolates from all samples will be reviewed for pathogen determination.

For subjects that have ABSSSI and blood specimens collected per protocol, baseline is defined as either Day -1 or 1. For subjects with cellulitis/erysipelas, if no acceptable baseline infectious material has been obtained or if no pathogens have been identified from the baseline sample, a Day 2 or 3 microbiological sample can be used as baseline if the sample is considered acceptable. If acceptable ABSSSI site and/or blood samples are obtained on both Study Days -1 and 1, all isolates will be reviewed for pathogen determination.

The 3 categories of pathogen classification are as follows:

1. Always a pathogen: If isolated from the culture of the ABSSSI, the following are always considered a pathogen:
 - Monomicrobial infections caused by
 - *Staphylococcus aureus* - isolates will be reviewed by oxacillin susceptibility results (methicillin resistant - MRSA and methicillin susceptible - MSSA) and MRSA and MSSA will be considered distinct pathogens.
 - Group A, B, C and G β -hemolytic streptococci (ie, *Streptococcus agalactiae*, *Streptococcus dysgalactiae*, *Streptococcus pyogenes*, etc.)
 - *Streptococcus anginosus* group (eg, *Streptococcus anginosus*, *Streptococcus intermedius*, *Streptococcus constellatus*)
 - *Enterococcus faecalis* - isolates will be reviewed by vancomycin susceptibility results (vancomycin resistant *Enterococcus faecalis* and vancomycin susceptible *Enterococcus faecalis*) and these will be considered distinct pathogens.
 - *Enterococcus faecium* - isolates will be reviewed by vancomycin susceptibility results (vancomycin resistant *Enterococcus faecium* and vancomycin susceptible *Enterococcus faecium*) and these will be considered distinct pathogens.
 - *Staphylococcus lugdunensis*
 - Gram positive anaerobes isolated from a major abscess or wound infection
 - Polymicrobial infection consisting of any combination of *Staphylococcus aureus*, Group A, B, C and G β -hemolytic streptococci and *Streptococcus anginosus* group
2. Never a pathogen: If isolated from the culture of the ABSSSI, the following are never a pathogen:
 - *Corynebacterium* spp.
 - *Bacillus* spp.
 - *Diphtheroids*
 - *Micrococcus* spp.
 - *Propionibacterium* spp.
 - *Actinomyces* spp.
 - *Actinobaculum* spp.
 - *Porphyromonas* spp.

- All coagulase-negative staphylococci with the exception of *S. lugdunensis* (eg, *S. capitis*, *S. caprae*, *S. cohnii*, *S. condiment*, *S. epidermidis*, *S. haemolyticus*, *S. hominis*, *S. saprophyticus*, *S. sciuri*, *S. simulans*, *S. warneri*, *S. xylosus*)
 - Gram positive anaerobes isolated from cellulitis/erysipelas
 - *Candida* spp., *Aspergillus* spp., or other fungi
3. Case-by case review: The following organisms will be assessed on a case-by-case basis via manual review by the Sponsor. If needed, subject clinical (eg, type of infection, type of specimen, subject underlying conditions, etc.) and microbiological information (eg, amount of culture growth, etc.) will be used to assist in determining if the isolate is a pathogen.
- Monomicrobial infection with an organism not listed in #1 or #2 above
 - Polymicrobial infections (infections with ≥ 2 pathogens) will be reviewed on a case-by-case basis, except as noted above for always a pathogen.
 - All organisms isolated from a blood culture
 - All Gram-negative organisms

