22.1 Analysis Populations

A number of subject analysis populations have been defined for the various analyses of efficacy and safety, as follows:

- The intent-to-treat (ITT) population will consist of all randomized subjects.

- The modified intent-to-treat (mITT) population will consist of all randomized subjects without a sole Gram-negative causative pathogen(s) at Screening.
- The clinically evaluable (CE) population will consist of all mITT subjects who received test article, have a qualifying ABSSSI, an assessment of outcome, and meet all other evaluability criteria detailed in the SAP.
- The microbiological modified intent-to-treat (micro-mITT) population will consist of subjects in the mITT population who have at least 1 Gram-positive causative pathogen(s) at Screening.
- The microbiologically evaluable (ME) population will include subjects in the CE population who have at least 1 Gram-positive causative pathogen(s) at Screening.
- The safety population will consist of all randomized subjects who receive test article.

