6.2 Evaluability Review Team

6.2.1 Membership and Responsibilities

The Evaluability Review Team (ERT) will review both clinical and microbiological data for determination of criteria used to assess inclusion in the analysis populations and for determination of baseline and post-baseline pathogens. ERT members will be blinded to treatment assignment and will review the data concurrent with the conduct of the study. The ERT will be conducted in accordance with the ERT process documents.

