8.2 Baseline Definition

In general, baseline is defined as the value closest to but prior to the initiation of test article administration. If no test article is received, baseline is defined as the value closest to but prior to randomization.

For pathogen determination, baseline is defined as either Day –1 or 1. For subjects with cellulitis/erysipelas, if no acceptable baseline infectious material has been obtained or if no pathogens have been identified from the baseline sample, a Day 2 or 3 microbiological sample can be used as baseline if the sample is considered acceptable. If no test article is received, for pathogen determination, study day is defined based on date of randomization.

For analyses of vital signs and ECGs, if no value is available prior to the initiation of test article administration, a value within 2 hours after initiation of test article administration can be used as baseline.

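### For cellulitis/erysipelas, an on-treatment Day 2–3 culture can count as baseline and so decide membership of the primary mITT or the micro-mITT population; the SAP does not declare this as a change from the protocol

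*SAP*

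**What the plan says.** Protocol 22.1 defines mITT as "all randomized subjects without a sole Gram-negative causative pathogen(s) at Screening", and ties micro-mITT to a Gram-positive pathogen at the same time point. Screening is a 24-hour phase completed before randomization (Protocol 14.2 and the footnotes to Section 8), and Day 1 is the day of the first dose.

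SAP 6.1.3 reads: "The mITT population will consist of all randomized subjects without a baseline sole Gram-negative ABSSSI pathogen. Pathogen determination is described in Section 6.1.4". In SAP 6.1.4, for specimens collected per protocol, "baseline is defined as either Day -1 or 1". That section then makes an exception for cellulitis/erysipelas: if there is no acceptable baseline material, or the baseline sample yielded no pathogen, "a Day 2 or 3 microbiological sample can be used as baseline if the sample is considered acceptable". SAP 8.2 repeats the exception ("if no pathogens have been identified from the baseline sample, a Day 2 or 3 microbiological sample can be used as baseline"), directly after its own general rule: "In general, baseline is defined as the value closest to but prior to the initiation of test article administration".

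SAP 6.1.4 lists "All Gram-negative organisms" among the isolates judged case by case. SAP 7 states that nothing has changed from the analyses in the protocol.

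**The concern.** Membership of the population for the confirmatory test should rest on information fixed before treatment. Here it can rest on a culture taken after one or more doses, which the drug itself may have altered. There are two routes:

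- **mITT.** A sole Gram-negative isolate from Day 2–3, if judged a pathogen, takes a randomized subject out of the primary denominator. The CE populations inherit this because they require mITT membership.
- **micro-mITT.** A Gram-positive isolate from Day 2–3 brings a subject into micro-mITT, and possibly ME. It does not change mITT.

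Nor does every subject have a Day 2–3 culture. The Protocol Section 8 flowchart has on-treatment cultures taken only when clinically indicated, and Protocol 13.2.3 allows planned procedures up to 48 hours after the start of test article. The documents therefore do not show whether the subjects sampled would be poor responders. Day 3 is also the visit at which Early Clinical Response is measured.

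The direction of any bias is not fixed. Removing failures from omadacycline favours non-inferiority, and removing them from linezolid works against it. Protocol 9.1 reports omadacycline activity against some Gram-negative organisms. If that matters, surviving Gram-negative isolates are likelier on linezolid.

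**Working it through.** **Is the conflict real?** Day 2 and Day 3 fall after the first dose, so they cannot be Screening. The rule appears in two SAP sections, so it is not a slip. The cross-reference in SAP 6.1.3 carries it into mITT, the population for the primary analysis in SAP 10.1. SAP 7 does not mention it.

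**The plan's own figure.** Inputs from SAP 5.1.1: success rate 79% in both arms, margin Δ = 0.10, one-sided alpha 0.025, power 90%. Farrington–Manning, per arm:

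n = [(1.960·s0 + 1.2816·s1)/Δ]²

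where s1 = √(2 × 0.79 × 0.21) = 0.576, and s0 ≈ 0.580 from the maximum likelihood estimates restricted to a difference of −0.10. This gives n = 351.5, so 352 per arm and 704 in total, as stated. The concern does not change this: the plan counts every randomized subject in mITT.

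**Sensitivity of the interval.** Unstratified Miettinen–Nurminen 95% limits as in SAP 10.1, with 278/352 successes (79.0%) in each arm. The numbers removed are assumptions, and every removed subject is taken to be a failure.

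| Removed | Comparison (omadacycline v linezolid) | 95% CI (%) |
|---|---|---|
| none | 278/352 v 278/352 | −6.04 to 6.04 |
| 1 omadacycline | 278/351 v 278/352 | −5.81 to 6.26 |
| 5 omadacycline | 278/347 v 278/352 | −4.87 to 7.14 |
| 1 linezolid | 278/352 v 278/351 | −6.26 to 5.81 |
| 5 linezolid | 278/352 v 278/347 | −7.14 to 4.87 |

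Each subject moves the lower limit by a little over 0.2 points. Near the margin one subject can decide the result: 264/352 v 278/352 has a lower limit of −10.20% (non-inferiority not met), while 264/351 v 278/352 has −9.98% (met).

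**Sensitivity of the type I error.** True rates at the margin (69% v 79%), 352 per arm. The probability that the score statistic at −10% exceeds 1.96 is summed exactly over both binomial distributions, after dropping the stated number of failures from the denominators.

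| Failures removed | From omadacycline only | From linezolid only |
|---|---|---|
| 0 | 0.0249 | 0.0249 |
| 1 | 0.0289 | 0.0216 |
| 2 | 0.0337 | 0.0183 |
| 3 | 0.0384 | 0.0158 |
| 5 | 0.0504 | 0.0112 |

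Removing 3 failures from each arm gives 0.0249. If 1, 3 or 5 omadacycline subjects are removed regardless of outcome, so that they fail at the arm's own rate, the error stays at 0.025. The effect therefore needs removal that is related to outcome and unequal between arms.

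**micro-mITT.** The documents give no size for this population. Assuming 150 to 300 per arm and 80% early response, adding one non-responder to 300 changes 240/300 = 80.0% to 240/301 = 79.7%. Adding five to 150 changes 120/150 = 80.0% to 120/155 = 77.4%. The arm's rate falls by 0.3 to 2.6 points.

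**The case against.** **The mITT route needs a long chain of events.** The subject must have cellulitis/erysipelas and no usable or positive baseline sample. A further culture must be taken on Day 2–3 by a valid technique, and it must grow a Gram-negative organism alone. Review must then judge that organism a pathogen. This stands: few subjects, perhaps none, will be affected. The type I error figures are worst cases, and on the Gram-negative activity argument the likelier direction is conservative.

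**The review is blinded.** SAP 6.2.1 says "ERT members will be blinded to treatment assignment". That guards against reviewer bias. It does not help if the drug changed the culture result, or if the subject's course determined who was cultured.

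**Other outputs would expose a problem.** SAP 9.1 tabulates reasons for exclusion from each population, SAP 9.2.1 lists all isolates, and SAP 10.4 analyses Early Clinical Response in ITT, which does not depend on pathogens. These help, but SAP 9.1 does not promise to flag Day 2–3 cases, and the ITT analysis is descriptive with no non-inferiority conclusion.

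**The protocol leaves population definitions to the SAP.** Protocol 22 does so, and the rule is prespecified. The fault is therefore an undeclared change, not an unauthorized one. The protocol's explicit reference to Screening remains, and the statement in SAP 7 is inaccurate.

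**Day 1 cultures are pre-dose if done on schedule.** Largely true. However, SAP 8.2 states the Day −1 or 1 rule without limiting it to specimens collected per protocol, and planned procedures may follow the first dose. A post-dose Day 1 sample is therefore not ruled out.

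**micro-mITT carries no confirmatory test.** Correct. What is affected there is the secondary objective of response by pathogen, together with the baseline MIC tables.

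**Conclusion.** The concern holds. The SAP lets a post-randomization, on-treatment observation define membership of the primary population. This departs from the protocol's wording and from the SAP's own general baseline rule, and SAP 7 does not declare it.

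The wording conflict is certain; the consequence is not. The documents give no count of affected subjects, the mITT effect is probably small and could be nil, and its direction is unknown. The upper end of the illustration (type I error 0.050) requires five removals, all failures and all from omadacycline. Planned sample size and power are not in question. The change is still worth making because it is cheap and removes a possible bias from the confirmatory analysis.

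**What to change.** Amend SAP 6.1.3, 6.1.4 and 8.2 as follows:

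1. Only isolates from samples collected before the first dose (before randomization if never dosed) can exclude a subject from mITT. Use the same wording in place of the Day −1 or 1 calendar rule, which has no dose-time cut-off.
2. Define the main micro-mITT population, and hence ME, from pre-dose isolates. Use Day 2–3 cellulitis/erysipelas isolates only in a supportive micro-mITT analysis.
3. If the Day 2–3 rule is kept for micro-mITT, declare it in SAP 7, report the affected subjects by arm, and show results without them. Also say how the rule fits with SAP Table 6, which treats a non-baseline pathogen isolated between Day 1 and EOT in a clinical failure as superinfection.

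The cost is wording in three SAP sections, plus a line in SAP 7 if the rule is kept. The main micro-mITT would lose a few subjects: those with cellulitis/erysipelas whose only isolate is from Day 2–3, and any subject whose only positive sample was taken on Day 1 after the dose. The change should be made before unblinding.
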